	
medicated), the SYNERGY stent system or protocol-required concomitant medications (e.g., everolimus or structurally related compounds, polymer or individual components, all P2Y12 inhibitors and aspirin)
 
 
7. Subject with implantation of a drug-eluting stent within 9 months prior to index procedure
 
8. Subject previously treated at any time with intravascular brachytherapy
 
9. Subject has an active peptic ulcer or active gastrointestinal (GI) bleeding
 
10. Subject is participating in an investigational drug or device clinical trial that has not reached its primary endpoint (Note: registry, observational, data collection studies are not exclusionary)
 
11. Subject intends to participate in an investigational drug or device clinical trial within 15 months following the index procedure (Note: registry, observational, data collection studies are not exclusionary)
 
12. Subject judged inappropriate for discontinuation from P2Y12 inhibitor use at 3 months, due to another condition requiring chronic P2Y12 inhibitor use
 
13. Subject with planned surgery or procedure necessitating discontinuation of P2Y12 inhibitor within 3 months following index procedure
 
14. Subject is a woman who is pregnant or nursing
 
15. Subject with a current medical condition with a life expectancy of less than 15 months
 
16. Target lesion(s) is located in the left main
 
17. Target lesion(s) is located within 3 mm of the origin of the left anterior descending (LAD) coronary artery or left circumflex (LCx) coronary artery by visual estimate
 
18. Subject has unprotected left main coronary artery disease (> 50% diameter stenosis)
 
19. Planned treatment of more than 3 lesions
 
20. Planned treatment of lesions in more than 2 major epicardial vessels
 
21. Target lesion(s) treated that involves a complex bifurcation (i.e. bifurcation lesion requiring treatment with more than one stent)
 
22. Target lesion(s) is restenotic from a previous stent implantation
 
23. Target lesion(s) is located within a saphenous vein graft or an arterial graft
 
24. Target lesion(s) with a TIMI flow 0 (total occlusion) or TIMI flow 1 prior to guide wire crossing
 
25. Thrombus, or possible thrombus, present in the target vessel (by visual
 

--	---

	estimate)

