**Table 9.3-1: Exclusion Criteria**

Exclusion Criteria
	
 
12. Subject judged inappropriate for discontinuation from P2Y12 inhibitor use at 3 months, due to another condition requiring chronic P2Y12 inhibitor use
 
13. Subject with planned surgery or procedure necessitating discontinuation of P2Y12 inhibitor within 3 months following index procedure
 
14. Subject is a woman who is pregnant or nursing
 
15. Subject with a current medical condition with a life expectancy of less than 15 months
 
16. Target lesion(s) is located in the left main
 
17. Target lesion(s) is located within 3 mm of the origin of the left anterior descending (LAD) coronary artery or left circumflex (LCx) coronary artery by visual estimate
 
18. Subject has unprotected left main coronary artery disease (> 50% diameter stenosis)
 
19. Planned treatment of more than 3 lesions
 
20. Planned treatment of lesions in more than 2 major epicardial vessels
 
21. Target lesion(s) treated that involves complex bifurcation (i.e. bifurcation lesion treated with more than one stent)
 
22. Target lesion(s) is restenotic from a previous stent implantation
 
23. Target lesion(s) is located within a saphenous vein graft or an arterial graft
 
24. Target lesion(s) with a TIMI flow 0 (total occlusion) or TIMI flow 1 prior to guide wire crossing
 
25. Thrombus, or possible thrombus, present in the target vessel (by visual estimate)
 

----------------------------------	---

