12.1.1.3. Statistical Methods

Death/MI:

A propensity score model with quintile adjustment will be used to address baseline imbalance between the test group and the historical control group. The null hypothesis will be tested against alternative hypothesis using the propensity score quintile adjusted death/MI co-primary endpoint for testing non-inferiority between the test group and the historical control group.

The propensity score will be estimated by using logistic regression with inclusion of all pre-specified baseline covariates in the model as the predictor variables and the treatment groups (test vs control) as the dependent variable.

The entire study analysis set will be divided into propensity score quintiles. The death/MI co-primary endpoints will be calculated by study group within each quintile. The adjusted measure for each study group is a simple mean of the five propensity score quintile estimates. Similarly, the stratified between-group difference estimate is the mean of the quintile difference estimates, and the adjusted standard error is obtained from the square root of the mean of the five quintile variances.

Let  $d_i, i = 1, \dots, 5$  be the quintile difference estimates,  $se_i, i = 1, \dots, 5$  are the standard errors of the quintile difference estimates, and  $var_i, i = 1, \dots, 5$  are the corresponding variances where  $var_i = se_i^2$ . The adjusted between-group difference estimate is  $\bar{d} = \frac{1}{5} \sum_{i=1}^5 (d_i)$ ,  $Var(\bar{d}) = \frac{1}{5^2} \sum_{i=1}^5 var(d_i)$ , and  $SE(\bar{d}) = \sqrt{Var(\bar{d})}$ .

The adjusted between-group difference estimate ( $\bar{d}$ ) and the standard error ( $SE(\bar{d})$ ) of the adjusted between-group difference will be used to construct the 97.5% upper confidence bound of the adjusted between-group difference using normal approximation to binomial (z-test). If the 97.5% upper confidence bound is less than the non-inferiority margin, the null hypothesis will be rejected for the death/MI co-primary endpoint and the test group will be concluded to be non-inferior to historical control group.

The covariates for propensity score model will include the following variables in different categories, which are available in both the short DAPT study and the historical control studies:

Table 12.1-1: Propensity Score Model Covariates

Category	Covariates
Geographic Location	region (US vs OUS)
Demographics	age, gender, race/ethnicity

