### 12.2.1. Analysis Sets

For the EVOLVE Short DAPT Study, a subject is considered enrolled once an informed consent form has been signed and the subject has received at least one commercial SYNERGY stent. Enrolled subjects must meet all inclusion and no exclusion criteria. The analysis set for the test group includes enrolled subjects who meet criteria for discontinuation of P2Y12 inhibitor and who discontinue P2Y12 inhibitor at 3 months. The analysis set will be used as the test group in the propensity score model.

For the death/MI co-primary endpoint analysis, the EVOLVE Short DAPT-like high risk for bleeding subjects will be extracted from HCRI DAPT, PE+ PAS, and PE PROVE studies to form the historical control group. For the secondary bleeding endpoint analysis, the EVOLVE Short DAPT-like high risk for bleeding subjects will be extracted from HCRI DAPT study only to form the historical control group. Bleeding events were not adjudicated by the CEC in the PE+PAS or the PE-PROVE study.

The EVOLVE Short DAPT-like subjects are defined as subjects who meet the EVOLVE Short DAPT Study inclusion criteria and do not meet any of the following exclusion criteria at the time of the index procedure:

- indication for the index procedure of acute ST elevation MI (STEMI) or Non ST elevation MI (NSTEMI),
- previously treated with intravascular brachytherapy,
- left main target lesion,

- more than 3 lesions treated,
- more than 2 vessels treated,
- bifurcations,
- in-stent restenosis,
- saphenous vein graft,
- TIMI flow 0 (total occlusion) or TIMI flow 1 prior to guide wire crossing, and
- thrombus or possible thrombus present in the target vessel (by visual estimate).

The high risk for bleeding subject set is defined as a set of subjects who meets one or more of the following criteria at the time of enrollment:  $\geq 75$  years of age and, in the opinion of the investigator, the risk of bleeding associated with  $>3$  months of DAPT outweighs the benefit, chronic or lifelong anticoagulation therapy, history of major bleeding (severe/life threatening or moderate bleeding based on the GUSTO classification) within 12 months of the index procedure, stroke (ischemic and hemorrhagic), or renal insufficiency (creatinine  $\geq 2.0$  mg/dl) or failure (dialysis dependent), and platelet count  $\leq 100,000$   $\mu\text{L}$ .

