### **BIFURCATION LESION**

A bifurcation lesion is a lesion associated with the area where a branch vessel  $\geq 2.0$  mm in diameter by visual estimate originates.

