**Revision History**

Revision Number	Release Date	Section	Change	Reason for Change
			required dual antiplatelet therapy (3 months of P2Y12 inhibitor, 15 months of aspirin)” to “Subject must be able to take study required dual antiplatelet therapy (as required per protocol).”	antiplatelet requirements for subjects taking chronic anticoagulants
AC to AD	June 20, 2016	Synopsis, Section 9.3, Section 12.2.1	Revision of exclusion criterion from “Planned treatment of more than 2 lesions” to “Planned treatment of more than 3 lesions.”	Revision to align exclusion criterion with pivotal study for SYNERGY
AC to AD	June 20, 2016	Synopsis, Section 9.3, Section 12.2.1	Addition of exclusion criterion “Planned treatment of lesions in more than 2 major epicardial vessels”	Revision to align exclusion criterion with pivotal study for SYNERGY
AC to AD	June 20, 2016	Synopsis, Section 9.3	Revision of two exclusion criteria “Target lesion(s) treated during the index procedure that involves a side branch $\geq$ 2.0 mm in diameter by visual estimate” and “Target lesion(s) treated during the index procedure that involves a clinically significant side branch $<$ 2.0 mm in diameter by visual estimate that has a clinically significant stenosis at the	Revision to align exclusion criterion with pivotal study for SYNERGY

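### Section 12.2.1 sets a broader bifurcation exclusion for historical controls than for test subjects, contradicts itself on anticoagulation, and leaves anticoagulated test subjects in the death/MI comparison

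*Combined protocol and SAP*

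**What the plan says.** **Control selection.** Section 12.2.1 takes controls from HCRI DAPT, PE+ PAS and PE PROVE for death/MI, and from HCRI DAPT alone for bleeding. Eligible controls are "defined as subjects who meet the EVOLVE Short DAPT Study inclusion criteria and do not meet any of the following exclusion criteria". The list that follows contains the single unqualified word "bifurcations".

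**Test selection.** Exclusion 21 in Table 9.3-1 covers a "complex bifurcation (i.e. bifurcation lesion treated with more than one stent"; the synopsis has "bifurcation lesion requiring treatment with more than one stent". Section 27.2 says "A bifurcation lesion is a lesion associated with the area where a branch vessel" of at least 2.0 mm originates. The number of stents plays no part in that definition.

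**Covariates.** Section 12.1.1.3 limits the propensity covariates to variables "which are available in both the short DAPT study and the historical control studies". Table 12.1-1 includes anticoagulant therapy. It has no bifurcation item, only possible proxies such as number of stents, CASS site, lesion length and reference vessel diameter.

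**Anticoagulation.** The high-risk definition in 12.2.1 still names chronic or lifelong anticoagulation. The current inclusion criteria (Table 9.2-1) do not, and exclusion 1 in Section 9.3 bars such subjects; that exclusion is not in the 12.2.1 list for controls. Section 11.10.1.1 lets anticoagulated subjects enrolled under a prior version qualify for P2Y12 discontinuation, so they can enter the test analysis set. Section 12.2.2 removes them from the second (bleeding) propensity model to compare like with like, and states no such removal for the first (death/MI) model.

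**The concern.** The death/MI comparison is non-randomised, so its credibility depends on the two groups being selected by the same rules, or on measured covariates that account for the differences. Three things fall short of that.

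1. As written, a subject with a one-stent bifurcation may be in the test group but not in the control group. This applies to both death/MI and bleeding, and no covariate records the feature directly.
2. A PE+ PAS or PE PROVE subject whose only high-risk feature is anticoagulation is a control under one sentence of 12.2.1 and not under another. Two programmers could extract different control groups for a co-primary endpoint.
3. Section 12.2.2 removes anticoagulated test subjects from the bleeding model because HCRI DAPT did not enroll subjects expected to stay on an anticoagulant. The same study supplies most death/MI controls, yet the plan gives no matching restriction or firm sensitivity analysis there.

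**Working it through.** **Step 1. Side-by-side reading.**

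| Item | Test group | Controls (12.2.1) |
|---|---|---|
| Bifurcation | Barred only if more than one stent (exclusion 21) | Barred without qualification |
| Lesion and vessel counts | At most 3 lesions, 2 vessels | Same |
| Anticoagulation as a high-risk qualifier | Not in the current inclusion criteria; prior-version subjects may remain | Listed in the high-risk definition, absent from the inclusion criteria that controls must meet |
| Anticoagulation as an exclusion | Exclusion 1 | Not listed |
| LAD/LCx origin lesion, unprotected left main disease, arterial graft | Barred (exclusions 17, 18, 23) | Not listed |

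The last row matters for direction: in those respects the control rule is the looser one.

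**Step 2. Reproduce the plan's sample size.** Inputs from 12.1.1.2: 5.6% in both groups, margin 2.52 points (0.45 × 5.6), one-sided 0.025, power 85%.

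n per group = (1.960 + 1.036)² × 2 × 0.056 × 0.944 / 0.0252² ≈ 1,495, against the plan's 1,500.

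Power = Φ(0.0252/SE − 1.96), with SE = √[0.056 × 0.944 × (1/nT + 1/nC)]. At 1,500 per group, SE = 0.00840 and power is 85.1%. At the planned 1,650 test subjects and 1,643 controls, SE = 0.00801 and power is 88.2%. Enrollment: 1,650/(0.85 × 0.97) = 2,001, against 2,000. The sample size is not in error.

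**Step 3. Where anticoagulated controls could come from.** HCRI DAPT share of death/MI controls: 1,240/1,643 = 75.5%. Other two studies: 403/1,643 = 24.5%. Overlap on chronic anticoagulation therefore rests largely on the 403.

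**Step 4. Bifurcation, illustration only.** The documents give no frequency or risk for one-stent bifurcations. Assume a share f of test subjects has one, with relative risk RR for death/MI, no adjustment through proxies, and controls at 5.6%. The shift in the test-minus-control difference is f × 5.6 × (RR − 1) points. Power uses the shifted test rate in the variance.

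| f | RR | Shift (points) | Power, 1,650 v 1,643 |
|---|---|---|---|
| 5% | 1.2 | +0.06 | 87% |
| 10% | 1.2 | +0.11 | 85% |
| 10% | 1.5 | +0.28 | 79% |
| 20% | 1.5 | +0.56 | 67% |
| 5 to 20% | 0.8 | −0.06 to −0.22 | 90 to 93% |

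A positive shift works against the test group, a negative one in its favour. The largest shift is 0.56/2.52 = 22% of the margin, at the extreme corner of the assumed range.

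**Step 5. Power of a death/MI analysis without anticoagulated subjects.** Assume 10 to 30% of the 1,650 test subjects and of the 403 controls are removed:

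- 10% and 10%: 1,485 v 1,603, power 86%
- 20% and 10%: 1,320 v 1,603, power 84%
- 30% and 30%: 1,155 v 1,522, power 80%

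These are unadjusted figures at 5.6% in both groups.

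**The case against.** **Shorthand.** The 12.2.1 list uses short labels, so the bifurcation entry may simply stand for exclusion 21. That is possible, but the text does not say so, and Section 27.2 gives the word a meaning that ignores stent count.

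**The revision log.** A reader might infer that the entry was overlooked when exclusion 21 was narrowed: the lesion-count and vessel-count rows name "Synopsis, Section 9.3, Section 12.2.1", whereas the row beginning "Revision of two exclusion criteria" omits 12.2.1. This is weak evidence. The log's section lists are not exhaustive; the anticoagulation row names only the synopsis and Sections 9.2 and 9.3 but says text was edited throughout. The point rests on the conflict in the current text alone.

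**Anticoagulation has a purpose in 12.2.1.** Prior-version subjects are still in the study, so the high-risk set may need to describe them. This is reasonable, but 12.2.1 does not limit the item to them.

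**The two endpoints differ.** Bleeding has HCRI DAPT as its only control source, and the log gives anticoagulated subjects' higher bleeding risk as a reason for removing them. Death/MI draws on three studies, has an anticoagulant covariate and an outcome-blinded modelling team, and further enrollment of these subjects has been stopped for comparability. All of this mitigates in part. However, a covariate cannot supply comparable controls that are not in the data, and stopping enrollment does not remove subjects already included.

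**The 403 as a ceiling.** A reader might infer that only the 403 non-HCRI controls can provide overlap. Section 12.2.2 does not support that. It describes long-term users expected still to be on an anticoagulant at randomization, and does not say that subjects expected to stop were barred.

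**The separate SAP.** It is cited but not part of the supplied text, and may already contain the sensitivity analysis. That would not resolve the conflict within 12.2.1.

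**Conclusion.** The inconsistency is real and affects who counts as a control for a co-primary endpoint. The bifurcation rule differs between groups as written. The anticoagulation item contradicts the inclusion requirement in the same section. The like-with-like step taken for bleeding has no death/MI counterpart, although 75.5% of death/MI controls come from the study that motivated it.

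A stronger reading is tempting: that controls are selected for simpler lesions, so that the comparison is biased in a known direction. The documents do not support it. Section 12.2.1 also omits the test exclusions for LAD/LCx origin lesions, unprotected left main disease and arterial grafts, so net lesion complexity is undetermined. Nor is there support for saying that false non-inferiority becomes more likely: if one-stent bifurcations or anticoagulation raise death/MI risk, these two mismatches would usually cost power instead. The power and shift figures rest on assumed shares and relative risks and are illustrative only. This should be corrected before endpoint analysis; it does not invalidate the design.

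**What to change.** (a) In 12.2.1, limit the bifurcation item to bifurcation lesions that received more than one stent. Have the outcome-blinded team re-extract controls before endpoint analysis, and update the approximate counts of 1,643 (death/MI) and 1,240 (bleeding). If a control study did not record stents per bifurcation, keep its exclusion of all bifurcations, say so, and run a sensitivity analysis without bifurcation subjects in the test group, provided the test data identify them.

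(b) Reconcile the anticoagulation item in 12.2.1 with Sections 9.2 and 9.3, and state whether it applies to controls or only to test subjects enrolled under prior versions.

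(c) Report anticoagulated counts by group within each propensity quintile. Pre-specify one death/MI sensitivity analysis that excludes chronic anticoagulation from both groups, with the propensity model refitted.

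**Cost.** A few lines of text, one re-extraction, one table and one or two sensitivity analyses. Enrollment and the primary test set do not change, but the control pool and its counts may. Some control events are already known (the synopsis gives 13/253, 14/318 and 11/85 for PROMUS subjects), so the re-extraction rule must be fixed and documented before it is applied. The anticoagulation analysis has somewhat less power than the primary one: about 80 to 86% unadjusted under the assumed shares, against 88%.

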**11.10.1.1. Eligible for Discontinuation of P2Y12 Inhibitor at 3 Months**

Subjects are eligible for discontinuation of P2Y12 inhibitor at 3 months if they meet both of the following criteria:

- Subject was treated with 3 months of P2Y12 inhibitor/aspirin post index procedure. (Subjects enrolled under a prior version of the protocol who were on chronic anticoagulation between 0-3 months are eligible if they were also taking P2Y12 inhibitor or P2Y12 inhibitor/aspirin between 0-3 months).
- Subject was free from events (stroke, MI, PCI, CABG, and stent thrombosis) between the index procedure and the 3-month visit

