**11.10.1.2. Not Eligible for Discontinuation of P2Y12 Inhibitor at 3 Months**

Subjects are not eligible for discontinuation of P2Y12 inhibitor at 3 months if any of the following criteria are met:

- Subject who experiences a stroke, MI, PCI, CABG and/or stent thrombosis, during the 0-3 month period (between the date of index procedure and the date of the 3-month follow-up visit)
- Subject who is non-compliant with P2Y12 inhibitor or aspirin during the 0-3 month period (between the date of the index procedure and the date of the 3-month follow-up visit). Subjects enrolled under a prior version of the protocol who were on chronic anticoagulation between 0-3 months are not eligible if they were not taking P2Y12 inhibitor or P2Y12 inhibitor/aspirin between 0-3 months.

Non-compliant defined as:

- Taking less than 80% or greater than 120% (subject reported); and/or

- Interruption for 14 or more consecutive days
- Subject judged inappropriate for discontinuation from P2Y12 inhibitor use at 3 months due to another condition requiring chronic P2Y12 inhibitor use

Compliance to the use of P2Y12 inhibitor and aspirin will be ascertained from the subject interview at the 3-month follow-up visit and will be used to determine if the subject is eligible for discontinuation of P2Y12 inhibitor. During the interview, the subject will also be asked about any significant interruptions (3 days or greater) in the prescribed treatment since the last follow-up visit.

Note: All enrolled subjects who receive a SYNERGY stent must be followed at all milestones through 15-months, regardless of eligibility to discontinue P2Y12 inhibitor.

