#### **12.3.4. Justification of Pooling**

An assessment of the poolability of 3-month eligible subjects across sites will be performed based on:

- 1) the co-primary endpoint of all death/MI for the test group,
- 2) the co-primary endpoint of all death/MI for the control group,
- 3) the co-primary endpoint of ARC ST for the test group,
- 4) the secondary endpoint of bleeding for the test group, and
- 5) the secondary endpoint of bleeding for the control group

using logistic regression with site as a factor and co-primary endpoints as the outcome. Sites with fewer than 10 subjects enrolled will be combined into “virtual sites” based on geographic regions within United States, Europe, Japan, and Brazil, so that “virtual sites” have at least 10 subjects but no more than the largest enrolling site. If the two-sided P value for the site effect is  $\geq 0.15$ , it will be concluded that the site effect is not different across sites, and the site data can be pooled. If the two-sided P value for site effect is  $<0.15$ , site differences will be explored.

The poolability assessment of the treatment-by-site interaction based on the common sites enrolling both the 3-month eligible test subjects and the historical control subjects will be performed:

- 1) the co-primary endpoint of all death/MI for the 3-month eligible test/control subjects and
- 2) the secondary endpoint of bleeding the 3-month eligible test/control subjects.

An assessment of the poolability of subjects across sites will be made using logistic regression with treatment, site and the interaction of site by treatment as independent variables and co-primary endpoints as the outcome. The same model will be assessed for the secondary endpoint as the outcome. Sites with fewer than 10 subjects enrolled will be combined into “virtual sites” based on geographic regions within United States, Europe, Japan, and Brazil, so that “virtual sites” have at least 10 subjects but no more than the largest enrolling site. If the two-sided P value for the interaction coefficient is  $\geq 0.15$ , it will be concluded that the treatment effect is not different across sites, and the data can be pooled. If the two-sided P value for the interaction coefficient is  $<0.15$ , site differences will be explored.

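### Section 12.2.1 selects test subjects at month 3 but states no month-3 condition for historical controls; if controls who would fail it carry higher later risk, the death/MI comparison leans toward non-inferiority

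*Combined protocol and SAP*

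**What the plan says.** **Test group.** Section 12.2.1 defines it as "enrolled subjects who meet criteria for discontinuation of P2Y12 inhibitor and who discontinue P2Y12 inhibitor at 3 months". Section 11.10.1.1 requires: "Subject was free from events (stroke, MI, PCI, CABG, and stent thrombosis) between the index procedure and the 3-month visit". Section 11.10.1.2 makes ineligible a "Subject who is non-compliant with P2Y12 inhibitor or aspirin during the 0-3 month period" and a "Subject judged inappropriate for discontinuation from P2Y12 inhibitor use at 3 months due to another condition requiring chronic P2Y12 inhibitor use".

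**Control group.** Section 12.2.1 takes subjects from three earlier studies who meet the inclusion criteria and "do not meet any of the following exclusion criteria at the time of the index procedure", with high bleeding risk judged at enrollment. Section 12.2.2 builds both propensity models on these sets and adds no month-3 condition for controls.

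**Covariates.** In Table 12.1-1 the only items that reach past the procedure day are counts that include staged procedures and the type of P2Y12 inhibitor used in months 0 to 3. There is none for events or compliance in that period.

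**Endpoint denominator.** Section 12.1.1 counts subjects with death/MI between 3 and 15 months, or free of it for at least 425 days. The origin of the 425 days is not given.

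**Pooling.** Section 12.3.4 opens with "An assessment of the poolability of 3-month eligible subjects across sites will be performed based on" and lists the control group under it. It later names "the co-primary endpoint of all death/MI for the 3-month eligible test/control subjects". Between the two, when it describes the common sites, it attaches the 3-month term to the test subjects only and mentions the historical controls without it.

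**The concern.** The two groups enter the 3-to-15-month comparison by different routes. Test subjects have been filtered on what happened in the first three months; on the stated rule, controls have not. A subject with an early MI, stroke, repeat revascularization or stent thrombosis, or with poor compliance, leaves the test group but can stay in the control group. Adjustment for baseline covariates cannot be relied on to remove a difference that arises after baseline.

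The comparison is a co-primary non-inferiority test against a non-randomized control. If the unscreened controls have higher later risk, they raise the control rate and make the margin easier to meet. The rule therefore needs to be explicit before outcomes are seen.

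**Working it through.** **1. The plan's own figures (12.1.1.2).** Rate 5.6% in both groups, margin 2.52 points, one-sided 2.5%, power 85%:

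n = (1.960 + 1.036)² × 2 × 0.056 × 0.944 / 0.0252² = 1,495 per group, against 1,500 stated. Power at 1,500 per group is 85.1%. Enrollment: 1,650 / 0.85 / 0.97 = 2,001, against 2,000 stated. The figures reproduce.

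**2. Effect of unscreened controls.** From the plan: 1,650 test subjects, 1,643 controls, control rate 5.6%, margin 2.52 points. Assumed: f, the share of controls alive at month 3 who fail the month-3 criteria, and k, their later relative risk. No propensity strata are modelled.

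- Rate in eligible controls: r = 0.056 / (1 − f + f·k)
- Shift = 0.056 − r
- True test rate at the null = r + 0.0252
- Type I error = Φ(shift / SE − 1.96), SE unpooled

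Example, f = 5%, k = 2: r = 0.056 / 1.05 = 0.0533; shift 0.27 points; null test rate 0.0785; SE = √(0.0785 × 0.9215 / 1,650 + 0.056 × 0.944 / 1,643) = 0.00872; Φ(0.00267 / 0.00872 − 1.96) = 4.9%.

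| k | f = 2% | f = 5% | f = 15% |
|---|---|---|---|
| 2 | 3.3% | 4.9% | 13.4% |
| 1.5 | 2.9% | 3.6% | 6.6% |
| 1 | 2.5% | 2.5% | 2.5% |
| 0.5 | 2.1% | 1.7% | 0.7% |

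At k = 2 the shifts are 0.11, 0.27 and 0.73 points. If covariate adjustment removed half the shift (assumed), k = 2 gives 2.9%, 3.5% and 6.2%. The 15% is the plan's allowance for ineligibility from all causes in the test group, so it is an upper case for controls.

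**3. The 425-day rule.** The last visit window closes 365 + 30 = 395 days after the 3-month visit, so the 425 days cannot run from that visit. If they run from index, controls who die before month 3 drop out, and so do controls with an early MI and no later event. Controls with an early MI and a later event stay. With early-MI share m and later risk q (both assumed), the rule adds

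[0.056(1 − m) + mq] / [(1 − m) + mq] − [0.056(1 − m) + mq].

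This is about 0.05, 0.10 and 0.15 points for m = 1%, 2% and 3%. At m = 2% it moves only from 0.108 to 0.091 points as q goes from 5.6% to 25%.

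**4. Why the landmark needs care.** A test subject must be event-free up to the visit, which may be as late as 120 days after the index or staged procedure. If the test count started at day 90, the days between would be event-free by construction. At a constant hazard this spares the test group 0.056 × 30/365 = 0.46 points if every visit is at day 120. If visits are uniform over days 83 to 120, the mean excess is 30²/2/37 = 12.2 days, or 0.19 points. By the formula in step 2, shifts of 0.19 to 0.46 points give type I error of about 4.1% to 7.7%. A staged procedure may take place up to day 7, so the latest visit is day 127 from index.

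**5. Power after screening.** Power = Φ(0.0252 / √(0.056 × 0.944 × (1/1,650 + 1/n₀)) − 1.96): n₀ = 1,643 gives 88.2%; 1,610 gives 87.9%; 1,561 gives 87.4%; 1,397 gives 85.4%.

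**The case against.** The strongest reply is that the size is assumed throughout. That stands: f, k, the early-MI share and the half-adjustment are not in the documents, and the sign reverses for k below 1. A reader might infer that the comparison is known to be anti-conservative, or that 13.4% estimates its error rate. The documents support neither.

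Second, controls may already be screened. Section 12.2 refers to a study-specific Statistical Analysis Plan that could hold the rule. In the synopsis, the denominators behind the expected rate for the two sponsor studies, 318 + 85 = 403, equal the number of sponsor-study controls available, so those may be subjects already evaluable for 3 to 15 months. Section 12.3.4 can be read the same way, though its wording on common sites points the other way. All this is possible; no text says so.

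Third, safeguards exist. An independent team blinded to outcomes selects the propensity models before the endpoint analyses (12.2.2), the denominator removes deaths before month 3, and sensitivity analyses are allowed. Blinding does not supply a missing eligibility rule, the denominator does not screen for early stroke, PCI, CABG or non-compliance, and no sensitivity analysis is named for this. The revision history records the test-group definition as a regulator's recommendation; that supports selecting the test group at month 3 but says nothing about controls.

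Fourth, all enrolled subjects who receive the stent "must be followed at all milestones through 15-months, regardless of eligibility to discontinue P2Y12 inhibitor", so the later risk of ineligible test subjects will be observed. This is useful but indirect: the stent differs and they may have continued the P2Y12 inhibitor.

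**Conclusion.** The concern holds as an asymmetry in the stated rules together with an inconsistency between Sections 12.2.1 and 12.3.4. Followed as written, 12.2.1 compares month-3-selected test subjects with controls selected only at index or enrollment, and neither the covariates nor the denominator closes the gap.

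The direction is conditional: toward non-inferiority if ineligible controls have higher later death/MI risk, none if equal, reversed if lower. For an assumed relative risk of 2 and 2% to 5% of controls affected, unadjusted one-sided error is 3.3% to 4.9% against a nominal 2.5%. The 13.4% figure needs the test group's 15% to apply to controls. This should be fixed before outcomes are seen; confidence is medium because share and risk are unknown and a rule may exist outside the text reviewed.

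**What to change.** 1. In 12.2.1, require controls to be alive and free of stroke, MI, stent thrombosis, CABG and PCI from index to a stated month-3 landmark. Do not count staged procedures within 7 days of index, which the test group is allowed (Section 11.9); otherwise staged controls would be dropped while staged test subjects stay.
2. Start the 3-to-15-month count where each group's event-free screen ends: the 3-month visit in the test group, already the anchor for later visits, and a fixed day after the index or staged procedure in controls, for example day 90. Add a sensitivity analysis at the latest test visit day (120 days after the index or staged procedure, up to day 127 from index). Do not start the test count at day 90 while requiring event-free status to a later visit.
3. State the origin of the 425 days in 12.1.1, so that early-MI controls are not kept only when they have a later event.
4. Have the screen applied before modelling by someone who passes only the screened list, and no 3-to-15-month outcomes, to the blinded propensity team. Restate the control count.
5. Align 12.3.4 with 12.2.1, or bring the rule into 12.2.1 if it is held elsewhere.
6. Apply the compliance and chronic-P2Y12-need criteria to controls as a sensitivity analysis if the control studies recorded them; otherwise state the limitation.

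**Cost.** Wording, re-extraction from three studies and some lost controls. An assumed 2% to 5% loss leaves 1,610 to 1,561, with unadjusted death/MI power 87.9% to 87.4%. The 1,500 minimum is crossed at 1 − 1,500/1,643 = 8.7% loss; a 15% loss leaves about 1,397, with unadjusted power 85.4%. If the same screen is used for bleeding (2.19% against 4%), unadjusted power falls from 80.1% with 1,240 controls to 79.7% or 79.1% with 1,215 or 1,178, and to 76.8% with 1,054.
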